9.4.5 Imaging Safety Assessment

Not applicable.

9.5 Pharmacokinetics

Pharmacokinetic parameters (C_{min}, C_{max}, T_{max}, AUC (TAU), CLT/F) for DCV will be derived from plasma concentration versus time data on Day 10 (± 3 days). The observed trough plasma concentrations of DCV and SOF/metabolites (C_{trough}) will be assessed.

Table 9.5-1 lists the pharmacokinetic sampling schedule to be followed for the assessment of DCV and SOF/metabolites pharmacokinetics. On Day 10, when the serial PK sampling will be performed, treatment should be administered at the clinic and not taken at home. Likewise, on visits when trough PK samples are collected, treatment should be administered at the clinic after collection of the PK sample. The timing of the dose prior to the PK sample collection should be recorded. There is no restriction on food consumption with regard to dosing and PK sample collection. Detailed instructions for the pharmacokinetic blood collection, labeling, processing, storage, and shipping will be provided to the site in the procedure manual.

Table 9.5-1: Pharmacokinetic Sampling Schedule for DCV and SOF

Study Day of Sample Collection	Cohort	Time (Relative To Dosing) Hour	PK Blood Sample for DCV	PK Blood Sample for SOF/metabolites
Day 10 +/- 3 days	All Cohorts	0 (Predose)	X	X
	All Cohorts	00:30	X	-
	Cohorts 1, 2 only	01:00	X	-
	All Cohorts	02:00	X	-
	All Cohorts	04:00	X	-
	All Cohorts	08:00	X	-
Week 4	All Cohorts	0 (Predose)	X	X
Week 8	All Cohorts	0 (Predose)	X	X
Week 12 (EOT)	All Cohorts	0 (Predose)	X	X
Virologic Breakthrough ^a	All Cohorts	0 (Predose)	X	X

^a When confirming on-treatment virologic breakthrough, PK samples should be collected along with the HCV RNA samples

In addition, plasma samples will be archived for potential metabolite analysis, if the need arises and to the extent possible.

[REDACTED]

[REDACTED]

[REDACTED]

[REDACTED]

[REDACTED]

[REDACTED]

[REDACTED]

[REDACTED]

9.8.1 Additional Research Collection

This protocol will not include sample collection and/or residual sample storage for additional research (AR).

9.8.2 Other Assessments

9.8.2.1 HCV Virologic Resistance Testing

Plasma specimens for possible resistance testing will be collected at study visits indicated in [Table 2-1](#), [Table 2-2](#), and [Table 2-3](#).

Phylogenetic analyses will be performed on all available baseline NS5A sequences to confirm/determine the HCV genotype and subtype of each treated participant. NS5A resistance testing will be performed on all baseline samples. Resistance testing will be performed using population-based sequencing and may be performed by next-generation sequencing on samples from participants with HCV RNA $\geq 1,000$ IU/mL. This includes samples from all participants experiencing on-treatment failure or relapse, defined as:

- Virologic breakthrough, defined as confirmed $\geq 1 \log_{10}$ IU/mL HCV RNA on-treatment increase from nadir, **or** confirmed on-treatment increase in HCV RNA \geq LLOQ if HCV RNA previously declined to $<$ LLOQ (TD/TND);
- Relapse, defined as HCV RNA $<$ LLOQ (TND) at EOT followed by HCV RNA \geq LLOQ in any follow-up visit window;
- HCV RNA \geq LLOQ at any time point not meeting the definition of virologic breakthrough or relapse followed by a confirmed increase in HCV.

For participants who experience virologic failure, NS5A and NS5B resistance testing will be performed on samples that best approximate the time of failure, when HCV RNA levels are $\geq 1,000$ IU/mL. The respective baseline samples from these participants will also be tested. Genotype testing will also be performed on virologic failure samples collected close to the time of failure.

Further testing will occur at selected time points, if needed, using either storage specimens for resistance testing or other available stored specimens. Exploratory resistance testing to evaluate low frequency variants may be performed on subsets of samples depending on patterns of viral load response.

Note: With this revised protocol, resistance testing will not be performed on Baseline samples

9.8.2.2 Acceptability and Palatability Assessments of Daclatasvir Formulations

Participants/caregivers will be asked to complete a questionnaire regarding the acceptability and palatability (including a hedonic scale) of the DCV formulations in conjunction with the dose of DCV administered on Day 1, Treatment Week 4, and Treatment Week 12 (10 seconds, 1 minute,

and 5 minutes after taking the tablet(s)); DCV will be administered at the site on the visits. Specific instructions for the assessment tool and documentation of results will be provided to the sites.

After the participant has been dosed with DCV, any issue associated with the palatability of the investigational product should be reported as an adverse event (ie, spitting up).

9.8.2.3 Brief Questionnaire/Interim Phone Contacts

A brief questionnaire will be completed by the participant [or the participant's legally acceptable representative, parent(s), or legal guardian] on Day 1 to include the participant's e-mail address, name of the participant's primary care physician and 2 non-residing contacts in case the participant cannot be reached for their study assessments. This questionnaire, unless prohibited by local laws or regulations, will be reviewed for the confirmation or modification (as applicable) by the participant [or the participant's legally acceptable representative, parent(s), or legal guardian] at the end of treatment visit and all post-treatment follow-up visits.

During the post-treatment follow-up phase, sites will be required to perform an interim telephone contact with the participant [or the participant's legally acceptable representative, parent(s), or legal guardian] on a quarterly basis when the participant is not required to come for an in-office visit (ie, post-treatment Week 36, 60, and 84). The purpose of phone contacts is to verify the participant's continuation in the study and to confirm the date of the next study visit.

Note: Due to the early termination of the study, participants will perform an EOS visit and interim telephone contact will not be necessary after the EOS visit.

9.9 Health Economics OR Medical Resource Utilization and Health Economics

Health Economics/Medical Resource Utilization and Health Economics parameters will not be evaluated in this study.

10 STATISTICAL CONSIDERATIONS

10.1 Sample Size Determination

Note: Not Applicable due to the early termination of the study; a total of 5 participants will have been enrolled in the study into Cohort 1.

A minimum of 30 participants, assigned to 3 age descending cohorts, will be evaluated for the primary endpoint (PK) with at least 8 participants assessed in each age cohort.

The primary objective of this study is to evaluate the PK of DCV. The PK profile of DCV has been well characterized in the clinical development program and it has been noted that DCV is associated with predictable pharmacokinetics. The intra-participant variability for DCV C_{max} and AUC (INF) was assessed from clinical studies where single oral doses of DCV were administered with or without food and were estimated to be low with a % CV of 18% for C_{max} and 10% for AUC (INF). Similarly, the inter-participant variability in DCV C_{max} and AUC were assessed from clinical studies where single and multiple oral doses of DCV administered alone, and with or without food in some cases, was identified to be modest with % CV values of 37.5% for C_{max}

and 35% for AUC. PK will be assessed in all participants, however, due to the low observed variability in DCV exposure, assessment of the PK in the initial 5 participants per age cohort will provide the necessary information to match DCV exposures between adults and paediatric participants and either allow enrolment to be initiated in the next descending age cohort(s) or indicate that additional participants need to be enrolled in the cohort with a modified dose. Enrolment will continue in each cohort, after the initial 5 participants have completed their Day 10 assessments, to have a minimum of 8 evaluable participants in each cohort.

Descriptive summary statistics will be provided for the secondary endpoints in this study.

10.2 Populations for Analyses

For purposes of analysis, the following populations are defined:

Population	Description
Enrolled Participants	All participants who sign informed consent and are assigned a Participant Identification Number
Treated Participants	All enrolled participants who take at least 1 dose of study treatment.

10.3 Statistical Analyses

The statistical analysis plan will be developed and finalized before database lock and will describe the selection of participants to be included in the analyses, and procedures for accounting for missing, unused, and spurious data. Below is a summary of planned statistical analyses of the primary and secondary endpoints.

A description of the participant population will be included in the statistical output reported, including subgroups of age, gender and race.

Note: With the early termination of this study, previously collected data to address PK, SVR, and select safety assessments (e.g. AEs, laboratory tests, end of treatment subject status) will be reported only within adolescent participants 12 to <18 years of age. Given the small number of subjects enrolled in the study, no statistical analyses will be performed. Genotypic substitution(s) associated with virologic failure and the acceptability and palatability of the DCV formulations will not be reported. Likewise, an interim analysis will not be performed.

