
 To evaluate genotypic substitution(s) associated with virologic failure To assess the acceptability and palatability for the age-appropriate chewable tablet formulation, and acceptability for adult film-coated tablet 	
 Frequencies of NS5A and NS5B resistance-associated variants (RAVs) emergent at the time of virologic failure on treatment and during follow-up in non-responders Summary of responses from questionnaire assessing acceptability and palatability at Day 1, Week 4, and Week 12

[REDACTED]
	
[REDACTED]

[REDACTED]
	
[REDACTED]

Overall Design:

The study will be an open-label, single-arm, descending-age cohort trial evaluating the PK profile, safety, tolerability, and efficacy of DCV+SOF administered for 12 weeks to paediatric participants (3 < 18 years of age) with CHC virus infection.

Enrolment will begin with Cohort 1, followed by Cohorts 2 and 3.

- Cohort 1: 12 to < 18 years of age
- Cohort 2: 6 to < 12 years of age
- Cohort 3: 3 to < 6 years of age

Note: Due to the early termination of the study, only participants 12 to <18 years of age were enrolled in the study into Cohort 1; no participants will be enrolled in Cohorts 2 and 3.

Samples for assessment of DCV PK will be collected on Day 10 of the study. In each cohort, DCV PK will be evaluated after the initial 5 participants complete their Day 10 visit in order to determine if the target DCV exposure is achieved.

Enrolment in Cohorts 2 and 3 will be dependent on the availability of the European Commission (EC) approved SOF age appropriate dose and formulation for the corresponding age cohort.

Post treatment, participants will be followed for 12 weeks to assess sustained virologic response at Post-treatment Week 12 (SVR12) and then for an additional 2 years (96 weeks) as long-term follow-up to assess [REDACTED], durability of response, long-term safety, and the persistence of resistance variants in non-responders.

Note: With the early termination of this study, participants will not complete the initially planned 96 weeks of LTFU. As of 18 October 2019, all participants will have completed their Post Treatment Week 24 visit and approximately 41 to 53 weeks of post-treatment follow-up;

participants will be asked to return to the study site to perform an EOS visit upon approval of the revised protocol.

Number of Participants:

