4 OBJECTIVES AND ENDPOINTS

Table 4-1: Objectives and Endpoints

Note: With the early termination of this study, previously collected data to address PK, SVR, and select safety assessments (e.g. AEs, laboratory tests, end of treatment subject status) will be reported only within adolescent participants 12 to <18 years of age. The secondary objectives related to assessment of genotypic substitutions associated with virologic failure and the acceptability and palatability of the daclatasvir formulations and the exploratory objective regarding durability of response will not be reported.

Objectives	Endpoints

Primary
 
 To evaluate the PK profile of DCV in combination with SOF in children and adolescents aged 3 to <18 years of age 	
 Pharmacokinetic parameters (C_{min}, C_{max}, T_{max}, AUC (TAU), CLT/F) for DCV derived from plasma concentration versus time data on Day 10 (± 3 days) within a dosing interval. In Cohort 3 (ages 3 to < 6 years of age); PK parameters will be assessed using model-based analyses with 5 samples from each participant.

Secondary
 
 To assess the safety and tolerability of the DCV+SOF regimen in paediatric participants 	
 Frequencies of serious adverse events (SAEs), adverse events (AEs) leading to discontinuation of study therapy, AEs by intensity, and laboratory abnormalities by toxicity grade on treatment and during follow-up

 To determine the proportion of participants with SVR12 	
 Proportion of participants with HCV RNA <LLOQ (TD or TND) at post-treatment follow-up Week 12

 To evaluate genotypic substitution(s) associated with virologic failure 	
 Frequencies of NS5A and NS5B resistance-associated variants (RAVs) emergent at the time of virologic failure on treatment and during follow-up in non-responders

 To assess the acceptability and palatability for the age-appropriate chewable tablet formulation, and acceptability for adult film-coated tablet 	
 Summary of responses from questionnaire assessing acceptability and palatability at Day 1, Week 4, and Week 12

[REDACTED]
	
[REDACTED]

[REDACTED]
	
[REDACTED]

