10.3.1 Efficacy Analyses

Efficacy endpoints will be assessed for treated participants by age cohort and total.

The proportion of participants achieving SVR12 (HCV RNA <LLOQ, TND or TD at Post-treatment Week 12) will be presented along with the corresponding 95% exact binomial confidence interval (CI). The principal analysis method will compute SVR12 on all treated participants, and missing HCV RNA data at post-treatment Week 12 will be imputed using the Next Value Carried Backwards (NVCB) approach, i.e., missing HCV RNA data in the post-

treatment Week 12 window will be imputed using the next and closest available HCV RNA measurement after the follow-up Week 12 HCV RNA visit window. A sensitivity analysis will compute SVR12 on treated participants with observed HCV RNA at follow-up Week 12.

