10.3.2 Resistance Analyses

The frequencies of NS5A RAVs at baseline will be presented by genotype, and if applicable, by subtype, for responders (SVR12) and virologic failures with genotypable isolates.

The frequencies of newly emergent NS5A RAVs detected at virologic failure on treatment or during follow-up will be presented for virologic failures with genotypable isolates. Newly emergent substitutions are substitutions that were not detected at baseline.

Note: These data will not be reported because the prevalence of the relevant RAV varies from 4-10% and as such might not be detected at Baseline in a sample size of 5 participants. As of 18 October 2019, all participants had completed at least 41 weeks of post-treatment follow-up and none had experienced virologic failure.

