6.1 General Methods

All summarizes are presented by cohort and total, unless specified otherwise.

Continuous parameters are summarized using univariate statistics, i.e., number of participants (n), mean, standard deviation (SD), median, quartiles, minimum and maximum. Categorical parameters are summarized using counts and percentages, or counts and proportions depending on the endpoint.

In general, all confidence intervals (CIs) are 2-sided with 95% coverage, unless otherwise specified. CIs for binary endpoints are based on exact binomial distribution. CIs for continuous endpoints are based on the normal distribution.

Longitudinal summaries of efficacy, safety, and questionnaire endpoints use pre-defined analysis visit windows.

Laboratory test endpoints are determined from measurements analyzed at both local and central laboratories, and are summarized using both Système International (SI) and US standard units.

Frequencies and percentages of participants with events are presented for the following: relevant protocol deviations; interruptions of study therapy; non-study medications; AEs; laboratory test and ECG abnormalities. Multiple occurrences of the same event are counted once per participant selecting the worst event to summarize, unless specified otherwise.

By-participant listings are provided for select endpoints, and are sorted by cohort, site identifier, and subject identifier. Listings display all events regardless of study period unless otherwise specified. Select listings (e.g., AEs, laboratory tests) display temporal dosing status according to the GBS standard temporal dosing model.¹

Participants who move to another investigative site during the study are classified according to their original investigative site, country and geographic region.

Formats of tables, listings, and graphs are described in the Data Presentation Plan.

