6.5.1 Primary and Secondary Efficacy Endpoints

6.5.1.1 SVR12

The proportion of treated participants with SVR12, defined as HCV RNA < LLOQ TD or TND at follow-up Week 12, are presented with 2-sided 95% CIs using the following 3 methods:

- Next Value Carried Backwards (NVCB): The numerator is based on participants meeting the response criteria, and the denominator is based on all treated participants. Participants with missing HCV RNA data at follow-up Week 12 have data imputed using the next and closest available HCV RNA measurement after the follow-up Week 12 HCV RNA visit window.
- Modified (mITT): The numerator is based on participants meeting the response criteria, and the denominator is based on all treated participants. Participants with missing follow-up Week 12 HCV RNA are counted as non-responders (i.e., missing data are not imputed).
- Observed values: The numerator is based on participants meeting the response criteria, and the denominator is based on treated participants with an evaluable HCV RNA measurement at follow-up Week 12 (i.e., participants with missing data are excluded).

NVCB is the principal analysis method, whereas mITT and observed values are sensitivity analysis methods.

SVR12 treatment outcomes are summarized using NVCB in the following categories:

- Responder
- Non-responder
 - o Non-responder with HCV RNA < LLOQ TND at EOT
 - Relapser. Defined as HCV RNA < LLOQ TND at EOT and HCV RNA ≥ LLOQ at follow-up Week 12

 - Other non-responder. Defined as HCV RNA < LLOQ TND at EOT and missing HCV RNA at follow-up Week 12 and thereafter.

Percentages for relapse and other non-responders are calculated based on treated participants with HCV RNA < LLOQ TND at EOT.

- On-treatment failure
 - Virologic breakthrough. Defined as either (1) confirmed ≥ 1 log₁₀ IU/mL HCV RNA increase from nadir on treatment, or (2) confirmed HCV RNA ≥ LLOQ on treatment after HCV RNA < LLOQ TD or TND on treatment. Confirmed is defined as ≥ 2 consecutive measurements.

 - Other on-treatment failure
- o No post-baseline HCV RNA value

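### Does the termination note in Protocol 10.3 leave it open whether the exact 95% CI for SVR12 is reported?

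*Protocol*

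**What the plan says.** The note in Protocol Section 10.3 makes two statements. PK, SVR and selected safety data already collected will be reported for the adolescents. Then: "Given the small number of subjects enrolled in the study, no statistical analyses will be performed".

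Section 10.3.1 has no termination note. It still says that the SVR12 proportion "will be presented along with the corresponding 95% exact binomial confidence interval (CI", computed on all treated participants with next-value-carried-backwards (NVCB) imputation, plus a sensitivity analysis on observed values.

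SVR12 remains an objective. The note above Table 4-1 drops the resistance objective, the acceptability and palatability objective, "and the exploratory objective regarding durability of response will not be reported", but not SVR12.

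Section 10.1 contains the sentence "Descriptive summary statistics will be provided for the secondary endpoints in this study", but that section opens with a note declaring it not applicable after termination, so it does not settle the matter.

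The SAP asks for the interval as well. In Section 6.5.1.1 the SVR12 proportions "are presented with 2-sided 95% CIs using the following 3 methods", and Section 6.1 says that "CIs for binary endpoints are based on exact binomial distribution". The SAP has no termination text, however. It still plans three cohorts and at least 30 participants, so it cannot show what the later Protocol note was meant to remove.

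**The concern.** Read in sequence, the parent section cancels statistical analyses and its first subsection prescribes one. Three subsections that lost their content (10.3.2, 10.3.5.1 and 10.3.6) received their own notes, and 10.3.1 did not. That could suggest that 10.3.1 is still in force. One programmer might produce an SVR12 table with an interval and another without.

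The stake would be how SVR12 reads. The note gives small numbers as its reason, yet an exact binomial interval is valid at n = 5, and that is where it tells a reader most. A bare 5/5 looks like 100%, although it is compatible with much lower true response rates.

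**Working it through.** The plan states no interval, power or precision figure for SVR12, so there is nothing to reproduce. The check has two parts: what the text means, and how much the interval would say.

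**Text.** Section 10.3 introduces its subsections as the planned statistical analyses. They contain the following:

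| Protocol section | Output specified | Own termination note | Inferential element |
|---|---|---|---|
| 10.3.1 Efficacy | SVR12 proportion, exact 95% CI | None | The CI |
| 10.3.2 Resistance | Frequencies | Data not reported | None |
| 10.3.3 Safety | Frequencies | None | None |
| 10.3.4 PK | Descriptive statistics | None | None |
| 10.3.5.1 Acceptability and palatability | Summaries | Data not reported | None |
| 10.3.6 Interim | Timing; median exposure against a range | Not performed | None |

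The study has a single arm, and these sections contain no hypothesis test or comparison between groups. If descriptive output survives (the note keeps PK, SVR and safety), the SVR12 interval is the only item in the table that the sentence on statistical analyses can remove.

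The missing note in 10.3.1 fits this reading. The notes in 10.3.2 and 10.3.5.1 withdraw the data themselves, and the note in 10.3.6 withdraws the interim look. SVR data are still reported, so 10.3.1 needed no such note. The amendment also leaves superseded wording in place elsewhere. Sections 10.3.1 and 10.3.3 still call for results by age cohort and in total, although only one cohort exists. Section 9.8.2.1 keeps baseline resistance testing in its text above a note that withdraws it.

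**Size.** Inputs:
- Number enrolled: 5 (Section 10.1 note). I assume all five were treated.
- Virologic failures: by 18 October 2019 "none had experienced virologic failure" (Section 10.3.2 note).
- Follow-up: by that date "all participants will have completed their Post Treatment Week 24 visit" (Synopsis). Table 2-3 schedules HCV RNA at Week 24, so NVCB would normally have a later value if Week 12 were missing, and the principal denominator stays at 5.

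The exact (Clopper-Pearson) 95% limits for x responders out of n are:
- lower = 0.025 quantile of Beta(x, n − x + 1)
- upper = 0.975 quantile of Beta(x + 1, n − x), or 1 when x = n

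When x = n the lower limit solves Lⁿ = 0.025, so L = 0.025^(1/n).

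| Result | Lower | Upper |
|---|---|---|
| 5/5 | 0.025^(1/5) = 47.8% | 100% |
| 4/5 | 28.4% | 99.5% |
| 3/5 | 14.7% | 94.7% |

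At the sizes first planned, a full response would have given 0.025^(1/8) = 63.1% for 8/8 (the minimum per cohort) and 0.025^(1/30) = 88.4% for 30/30 (the minimum total).

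The chance of 5/5 at a true rate p is p⁵: 0.80⁵ = 32.8% and 0.70⁵ = 16.8%.

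Each row in the table of results follows from the reported count and n = 5 alone. Leaving the interval out withholds nothing that the count does not already give.

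**The case for a change.** The strongest case for a change is that the parent note cannot simply override everything below it. Section 10.3 labels all its subsections as statistical analyses, so a literal reading would also cancel the PK summaries and safety frequencies that the same note says will be reported. The sentence therefore needs a narrower meaning, and the Protocol does not spell one out. An added line saying that only comparisons and tests are dropped, and that the exact CI stays, would end the doubt and give readers an honest picture of five patients.

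Part of this stands. The Protocol does not state the narrower meaning, 10.3.1 was left un-annotated, and an exact interval at n = 5 is both valid and informative.

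The proposed line does not follow, however. There are no comparisons or tests to drop, so that wording would leave the sponsor's sentence with nothing to remove and would reverse its likely intent. Preferring an interval is a reasonable statistical view, but it disputes the sponsor's choice and does not expose an error. The cost is also more than a sentence. Appendix 2 (Compliance with the Protocol and Protocol Revisions) requires ethics committee approval of an amendment before a change is implemented, or notice to the committee if it is made by administrative letter. That is a lot of process for one derivable interval in a trial that is closing.

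**Conclusion.** The two sentences are in tension, but no change to the plan is needed. The most natural reading is that SVR12 is reported as a count and proportion, without the interval. An analyst who prints the interval anyway does no harm.

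Both readings give the same count out of 5. SVR12 is a secondary endpoint, PK is primary, and no rule in the plan uses the SVR12 interval. Error rates and sample size are unaffected. The whole difference is whether a line such as 47.8% to 100% appears beside 5/5, or 28.4% to 99.5% beside 4/5.

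These figures assume that all five enrolled participants were treated and that each has a usable HCV RNA value at or after Week 12. The 5/5 result is also an assumption: it agrees with the absence of virologic failure, but the documents state no SVR12 result. The stated rationale for the amended text is redacted, so the sponsor's intent is inferred from the wording. The conclusion does not depend on that inference, because neither reading alters the reported result.
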